9.2.6 End-Of-Study Follow-up Visit (Visit 8, around Day 189)

The Investigator will review the totality of the safety information including the most recent test results and take appropriate actions as necessary. Adverse events still ongoing at the time of the visit will be assessed and evaluated for further follow-up as necessary. The following will also be performed:

1. Return prior treatment boxes, for accountability purposes;
2. Vital signs and 12-lead ECG;
3. Complete physical examination;
4. Ophthalmological evaluation: The NVQ will be self-administered and a complete ophthalmological examination (includes dark adaptation tests). If clinically indicated by the ophthalmologist, an electroretinogram will also be performed;
5. Pulmonary function tests (FEV₁);
6. Blood sampling and urine collection for safety laboratory tests, pregnancy test if applicable, lipidomic tests, plasma retinol and retinol-binding protein;

7. Body weight, with BMI calculated;
8. For patients participating in the bone density exploratory assessment, they will undergo their post-study assessment;
9. Final CFQ-R questionnaire will be filled out;
10. At select sites participating in the investigation of the Matouk Disease Score, the final Score will be determined.

9.3 Pulmonary Exacerbation Reporting and Evaluation

Below is the protocol definition of a pulmonary exacerbation, based on patient reporting it to the Study Staff at the time of scheduled visits of the study or patient reporting it by communicating with the Study Staff between scheduled study visits. Patients will be provided with contact information cards to facilitate the reporting, which is deemed to be standard of care at the site. Since there are several PEx-related efficacy endpoints, all potential PEx-related signs and symptoms will be carefully documented in the specific e-CRF screening tool, in order to determine during the analysis phase if they met the protocol definition of PEx. A sample of this PEx screening tool can be found in the Sample Case Report Form.

If indeed these result in a suspicion of a PEx requiring IV antibiotic treatment or any need to attend the clinical site, the patient will be invited to the clinical site to complete the assessment and for the Study Investigator to determine if an intervention is required and in particular if a new antibiotic (oral or IV) is required to treat the signs and symptoms. This visit at the clinical site should be scheduled at the earliest convenience to avoid any worsening of the patient's condition, e.g. not waiting for the next scheduled study visit if it is not happening soon enough to ensure the proper standard of care. If the PEx happens when the clinical site cannot attend to it, then the patient may miss the pre-PEx visit and procedures without impacting study participation.

At the time of the visit, the site staff including the Study Investigator will confirm the previously reported signs and symptoms and any changes affecting them, as well as perform PEx assessments such as pulmonary function tests, oxygen saturation and measure weight. It will also be an occasion to review concomitant medications and update adverse events. The Study Investigator will determine the proper treatment, if any, for the signs and symptoms, all to be reported as adverse events, and if the Study Investigator determines that they constitute a PEx, they will also be reported as such in the e-CRF and the patient's records, along with the prescribed treatment. If an IV antibiotic course is required and the patient can attend the clinical study site prior to starting the IV antibiotics, then this will trigger the actions listed below in Section 9.3.2, prior to starting the first dose of IV antibiotics. The IV antibiotics may be administered at clinics more convenient for the patient, but under some oversight by the Study Investigator.

During the IV antibiotic treatment days, the patients should receive the proper Standard of Care. They should be informed that another study visit will happen immediately or shortly after completing the IV antibiotic course. That visit can coincide with the visit to the clinical site to receive the last dose of the IV antibiotic if indeed the antibiotic was administered at the clinical site.

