6 STUDY OBJECTIVES

Primary objectives:

- 1- To assess the safety and tolerability of LAU-7b in CF patients by the incidence of treatment emergent adverse events as compared to placebo; and
- 2- To assess the efficacy of LAU-7b as depicted by the absolute change from Baseline in FEV₁ percent predicted, relative to placebo-treated patients.

Secondary objectives:

- 1- To assess the normalizing effect of LAU-7b on the key lipidomic markers in plasma phospholipids, such as AA, DHA and the AA/DHA ratio;
- 2- To evaluate the efficacy of LAU-7b on other clinically relevant parameters, such as Time-to-first protocol-defined PEx and incidence of protocol-defined PEx, change in weight and BMI, usage of new antibiotics, and the change in CFQ-R;
- 3- To evaluate the change in selected systemic inflammation markers;
- 4- Determine if LAU-7b has an effect on lung colonization with *PsA*, as measured by CFU in sputum;
- 5- To explore the pharmacodynamics of LAU-7b on select systemic metabolipidomic markers, oxidative stress markers, bone formation/resorption, and ceramides subclass concentration;
- 6- To explore the change in plasma AA/DHA ratio, EPA, inflammation markers and FEV₁ between the start and the end of IV antibiotic treatment for PEx (performed only in patients who receive IV antibiotics for what their treating physician considers a PEx);
- 7- To explore clinical scoring using the Matouk Disease Scoreⁱⁱ.

Rationale for the selection of objectives:

This is a Phase II study that aims at gathering efficacy data as well as expanding and confirming the safety and pharmacodynamic information obtained during the Phase Ib study in adult CF patients.

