7.1.3 Secondary Endpoints

- The proportion of patients achieving normalization of AA, DHA and the AA/DHA ratio in plasma phospholipids, LAU-7b compared to placebo. In this study, the normalization means a value or ratio value reaching the mean observed in healthy controls ± 1 SD;
- The absolute and relative (%) change from pre-study in FEV₁ percent predicted on Days 21, 49, 77, 105 and 189 visits (3, 7, 11 and 15 weeks during treatment and approximately 4 weeks after treatment, respectively), as well as the relative (%) change in FEV₁ % predicted on Day 161 (24 weeks), LAU-7b compared to placebo;
- The effect on the time to first protocol-defined PEx, LAU-7b compared to placebo;
- The effect on the incidence of protocol-defined PEx, LAU-7b compared to placebo;
- The effect on the time to first antibiotic use (other than chronic inhaled antibiotics already started prior to trial or oral chronic azithromycin), LAU-7b compared to placebo;

- The effect on the number of antibiotic treatments (other than chronic inhaled antibiotics already started prior to trial or oral chronic azithromycin), LAU-7b compared to placebo;
- The effect on the number of days of antibiotic treatment (other than chronic inhaled antibiotics already started prior to trial or oral chronic azithromycin), LAU-7b compared to placebo;
- The change from pre-study in systemic markers of inflammation in whole blood (total white cell count and absolute neutrophil count), serum (hsCRP and serum amyloid A), and plasma (calprotectin, haptoglobin, IL-1ra, IL-6, IL-8 IL-10, G-CSF, ceruloplasmin and neutrophil elastase antiprotease complexes), LAU-7b compared to placebo;
- The changes from pre-study in body weight and BMI, LAU-7b compared to placebo;
- The overall change in the *PsA* density in the sputum, from baseline through 12 and 24 weeks of treatment, when measured by the difference in the Area Under the Curve (AUC) of the CFU, LAU-7b compared to placebo;
- The fenretinide steady-state pharmacokinetics, depicted by C_{min} plasma concentrations at the end of the first and sixth treatment cycle;
- To assess the impact on overall health, daily life, perceived well-being and symptoms measured with the CFQ-R (total and respiratory domain) from pre-study to 12 and 24 weeks, LAU-7b compared to placebo.

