9.3.1 Protocol Definition of a Pulmonary Exacerbation

The presence of a protocol-defined pulmonary exacerbation is defined by the following, the criteria of Fuch et al. ⁹⁴: "Exacerbation of respiratory symptoms": a patient treated with parenteral antibiotics for any 4 of the following 12 signs or symptoms:

Change in sputum	New or increased hemoptysis	Increased cough
Increased dyspnea	Malaise, fatigue or lethargy	Temperature above 38°C
Anorexia or weight loss	Sinus pain or tenderness	Change in sinus discharge

Change in physical
examination of the chest

Decrease in pulmonary function by
10 percent or more from a previously
recorded value

Radiographic changes indicative of
pulmonary infection

This definition is not a guide to determine the need for a given type of treatment (for example: Oral versus IV antibiotics, corticosteroids or no). Each Investigator will determine to the best of its clinical judgement and for the benefit to the patient, the best treatment for the exacerbation episode. However, if indeed an IV antibiotic course is selected based on the severity of the PEx and other factors and the patient can attend the study site prior to starting the IV antibiotics, this will trigger the performance of PEx-specific assessments prior to initiating the IV antibiotic course and at the end of the course. This is outlined below:

9.3.2 Specific additional testing for patients undergoing a pulmonary exacerbation treated with an IV antibiotic treatment cycle.

Prior to starting and after completing the IV antibiotic treatment:

1. Blood sampling for selective biomarkers such as:
 - a. Plasma lipidomics: AA, DHA, calculated AA/DHA ratio and EPA;
 - b. Markers of inflammation in:
 - Whole blood: total white cell count and absolute neutrophil count;
 - Serum: high sensitivity C-Reactive Protein (hsCRP) and serum amyloid A (SAA);
 - Plasma: interleukins IL-1ra, IL-6, IL-8, IL-10, Granulocyte-Colony Stimulating Factor (G-CSF), calprotectin, ceruloplasmin, haptoglobin, and neutrophil elastase antiprotease complexes (NEAPC).
2. Clinical parameters such as FEV₁ percent predicted, weight, with BMI calculated.

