9.3.3 Pulmonary Exacerbation Evaluation and Conventions

The duration of PEx antibiotic treatment, whether IV or Oral, should be set at the shortest possible duration achieving the desired eradication of infection and alleviation of the PEx symptoms. It should always be 7 days or more in duration. Corticosteroids, albeit authorized for the treatment of PEx episodes, should be reserved for the more severe cases and their usage (dose and duration) set to the minimum required.

For reporting purposes, a PEx episode is considered an adverse event and its severity should be commensurate with the type of treatment required. The following is the information required at a minimum when reporting a PEx episode; please refer to the PEx case report form for more details.

1. Precise dates of initial reporting by the patient to the study staff;
2. Date of appointment set to evaluate the PEx;
3. Complete list of items from the Fuch scale listed in Section 9.3.1 observed for the patient;
4. Investigator judgment on the Severity of the PEx episode;
5. Prescribed antibiotic treatment (name of medication, route of administration and planned duration of treatment) and other support medications (e.g. corticosteroids);
6. Record of PEx-related specific blood sampling for pre-antibiotic treatment biomarkers, body weight and BMI, if the prescribed antibiotic treatment is intravenous;
7. Record of PEx-related specific pre-antibiotic treatment FEV₁ value, if the prescribed antibiotic treatment is intravenous;
8. Precise record of initiation of intravenous antibiotic treatment, if applicable;
9. Record of PEx-related specific blood sampling for post-antibiotic treatment biomarkers, body weight and BMI, if the prescribed antibiotic treatment is intravenous;

10. Record of PEx-related specific post-antibiotic treatment FEV₁ value, if the prescribed antibiotic treatment is intravenous;
11. Actual time of completion of intravenous antibiotic treatment, if applicable;
12. Any other information required in the case report form.

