3.18 Analysis of the Safety Endpoints

For the purpose of analyses and tabulations, AEs will be classified as pretreatment AEs, TEAEs, or posttreatment AEs. More specifically: Pretreatment AE are those that started before the first dose of study drug. TEAE are those that increased in severity or appeared at or after the first dose of study drug and before or at the last follow-up, planned for 4 weeks after the last dose of study

drug. Post-treatment AEs are those that increased in severity or that appeared after the last follow-up, planned for 4 weeks after the last dose of study drug; these AEs will be reported by the Investigator to the sponsor and the appropriate regulatory agency, as well as treated and followed according to local regulations. Post-treatment AE's will be reported separately from the study's clinical study report.

For AEs with missing or incomplete start dates, if there is no clear evidence that the AEs started before or after the first dose of study drug, then the AEs will be classified as TEAEs.

TEAEs will be coded using the Medical Dictionary for Regulatory Activities (MedDRA) and the following information will be summarized:

- Overall TEAEs will also be described according to:
 - Seriousness (yes, no),
 - Severity (mild, moderate, severe, life-threatening),
 - Causality (definitely related, probably related, possibly related, not related),
 - Action taken with study drug (dose not changed, dose interrupted, drug withdrawn, not applicable),
 - Outcome (recovered / resolved, recovered / resolved with sequelae, not recovered / resolved, fatal, unknown).
- The total number of TEAEs, the total number and proportion of patients experiencing at least one TEAE during the treatment period will be summarized by system organ class (SOC) and preferred term (PT). TEAEs occurring with an incidence $\geq 10\%$ will be tabulated in a separate table. To count the number of patients who experience each TEAE, patients experiencing the same TEAE multiple times will only be counted once for the corresponding PT. TEAEs will be tabulated presenting the SOCs alphabetically. All TEAEs, and TEAEs occurring with an incidence $\geq 10\%$, will be presented overall as well as stratified by causality (Definitely Related, Probably Related, Possibly Related, Not Related).
- AE summary tables will be presented for TEAEs only and will include the following:
 - All TEAEs;

- TEAEs by relationship;
- TEAEs by maximal severity;

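### As written, each exacerbation and each of its signs becomes a separate adverse event, so the overall TEAE totals move with an efficacy outcome, and the SAP 3.18 text gives no summary without them

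*Protocol*

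**What the plan says.** **Recording rules.** Protocol 9.3 covers the visit for a suspected PEx. The investigator determines the treatment "for the signs and symptoms, all to be reported as adverse events, and if the Study Investigator determines that they constitute a PEx", they are also reported as that in the e-CRF and the patient's records. Protocol 9.3.3 adds: "For reporting purposes, a PEx episode is considered an adverse event and its severity should be commensurate with the type of treatment required". The same signs are also documented in a dedicated PEx screening tool in the e-CRF (9.3).

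**Definition.** Protocol 9.3.1 defines a protocol-defined PEx as "a patient treated with parenteral antibiotics for any 4 of the following 12 signs or symptoms".

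**Role in efficacy.** Protocol 7.1.3 lists as a secondary endpoint: "The effect on the incidence of protocol-defined PEx, LAU-7b compared to placebo".

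**Role in safety.** The first primary objective (Protocol 6) is to assess safety and tolerability "by the incidence of treatment emergent adverse events as compared to placebo". SAP 3.18 states: "The total number of TEAEs, the total number and proportion of patients experiencing at least one TEAE during the treatment period will be summarized". The breakdown is by system organ class and preferred term. It also plans tables of TEAEs with at least 10% incidence, by relationship, by maximal severity, leading to discontinuation, serious and fatal. Its only rule on repeats counts a patient once per preferred term. It states no version without PEx or its signs. SAP section 5 records that Fisher's exact test was dropped and that safety is assessed descriptively.

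**The concern.** One clinical event feeds both sides of the benefit-risk account. If LAU-7b lowers the PEx rate, its adverse event total falls because of efficacy, and each avoided episode takes several records with it. That fall can offset a real excess of drug-caused events in the overall totals. If LAU-7b has no effect on PEx, a block of records common to both arms dilutes the contrast.

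Entry criteria select patients likely to exacerbate (Protocol 6), and with no formal safety test the descriptive tables carry the safety conclusion. Overall counts have already been read this way: Protocol 5.4.4.1 and 5.4.4.3 remark that adverse events fell as the Phase Ib dose rose. The documents do not show that PEx caused that fall.

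**Working it through.** The plan gives no figure of its own on this point. The check is a reading of the rules followed by expected-count arithmetic.

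**Inputs from the documents**
- 136 randomized 1:1, so 68 per arm (Protocol 12.1).
- Risk of an IV-treated PEx in a 24-week study: about 30% with an IV-treated PEx in the prior year; the odds are said to drop by half without one (Protocol 6). Halving the risk gives 15%. Halving the odds gives 0.30/0.70 ÷ 2 = 0.214, and 0.214/1.214 = about 18%. Range used: 15% to 30%.
- At least 4 signs per protocol-defined PEx (Protocol 9.3.1).

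**Assumptions**
- One episode per affected patient, each IV-treated PEx carrying the 4-sign minimum.
- Oral-treated PEx left out, because no rate is given.

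**Records per episode.** 4 signs + 1 episode = 5. The once-per-preferred-term rule does not join different sign terms to each other or to the PEx term.

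**Records in 136 patients** = 136 × risk × records per episode

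| Risk | 1 record | 5 records |
|---|---|---|
| 15% | 20.4 | 102 |
| 30% | 40.8 | 204 |

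**Effect of an assumed 30% PEx reduction in one arm** = 68 × risk × 5 × 0.30
- 15%: 15.3 records
- 30%: 30.6 records

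**Share of all records** = PEx records / (PEx records + 136 × m), where m is other adverse events per patient, not given in the documents. At 5 records per episode:
- Lowest shown (15%, m = 8): 102 / (102 + 1,088) = 9%
- Highest shown (30%, m = 1): 204 / (204 + 136) = 60%

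**Can the direction reverse?** Illustration with every rate assumed: PEx 30% placebo and 20% active; drug-harm events 0.05 and 0.25 per patient; 2 other events per patient in both arms.
- 5 records: placebo 68 × (1.50 + 0.05 + 2) = 241; active 68 × (1.00 + 0.25 + 2) = 221.
- 1 record: placebo 68 × (0.30 + 0.05 + 2) = 160; active 68 × (0.20 + 0.25 + 2) = 167.

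The same harm appears as fewer events on active under the literal rule and as more events with one record per episode.

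**Patients with any TEAE.** Assume independent risks: 50% for other events, harm 5% placebo and 15% active, PEx as above.
- PEx included: 1 − 0.5 × 0.70 × 0.95 = 66.7% placebo; 1 − 0.5 × 0.80 × 0.85 = 66.0% active.
- PEx excluded: 1 − 0.5 × 0.95 = 52.5%; 1 − 0.5 × 0.85 = 57.5%.

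This row is moved by the PEx itself. A patient counts once whether 1 or 5 records exist.

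**Harm in its own preferred-term row.** 68 × 0.05 = 3.4 against 68 × 0.15 = 10.2 patients. It stays visible whatever is done with PEx.

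**The case against.** The case against has real substance.

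- **Distinct harms have their own tables.** SAP 3.18 tabulates by system organ class, preferred term and causality, and SAP 3.10 tabulates nyctalopia and hemeralopia separately. The DSMB pays particular attention to ocular and dermatological events (Protocol 7.2.2), and the expected eye and skin effects are not among the 12 signs. A fall in PEx records judged unrelated cannot cancel events in the drug-related table. This stands and confines the point to the summaries, and to harms that resemble a PEx sign, such as fatigue, anorexia or weight loss.
- **The multiplier acts on records, not patients.** This stands: extra sign records hardly move patient-level incidence.
- **PEx is a legitimate safety outcome.** Protocol 5.4 reports that earlier anti-inflammatory attempts led to frequent exacerbations, and SAP 3.18 lists change in PEx incidence as a safety evaluation. This stands, and is why the all-TEAE tables should remain.
- **Five records are not certain.** Reporting the PEx in the e-CRF could mean only the PEx form, and Protocol 11.1.2 prefers a diagnosis to an abnormal assessment. But 9.3.3 separately makes the episode an adverse event, and no text tells sites to replace PEx symptoms with the diagnosis. Double entry is the natural reading, though not beyond doubt.
- **No decision rule uses the total.** Trial success rests on FEV₁ (SAP 3.2 and 3.14). This limits the consequence, but TEAE incidence is still a stated primary objective.
- **The mock tables in SAP section 7 were not available for this review.** A table without PEx may exist there. If so, the SAP part of the point is already met.

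**Conclusion.** The point holds for the overall summaries. The literal recording rule turns one protocol-defined PEx into about 5 adverse event records, or about 102 to 204 records in 136 patients instead of 20 to 41. The total TEAE count is the most exposed; the any-TEAE, maximal-severity and serious summaries are affected less. Under assumed but unremarkable rates, the total can reverse direction.

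Three stronger readings are tempting and are not supported:
- **That the safety tables mostly count the efficacy outcome.** The share runs from 9% to 60% at the 4-sign minimum, depending on an adverse event rate the documents do not give. The efficacy outcome also requires parenteral antibiotics and 4 of 12 signs, whereas any PEx on investigator judgment is entered as an adverse event, so the two overlap without being identical.
- **That a 30% reduction could remove as many as 102 records from an arm.** That needs 1.0 PEx per patient at 5 records each (68 × 1.0 × 5 × 0.30). It would have to include oral-treated episodes, which have no stated rate and no 4-sign minimum. The protocol's own risks support about 15 to 31.
- **That drug harm in general would be hidden.** Offsetting is confined to the summaries named above.

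The sizes rest on one episode per affected patient, the 4-sign minimum, literal double entry and an assumed 30% PEx reduction.

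**What to change.** **Protocol 9.3 and the e-CRF completion guide.** Record each investigator-confirmed PEx as one adverse event, the diagnosis. Keep its component signs in the existing PEx tool. Still report separately any sign that the investigator considers possibly drug-related or not explained by the PEx, so that fatigue or anorexia due to drug is not lost.

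**SAP 3.18.** Beside the all-TEAE tables, add the summary tables (any TEAE, total count, maximal severity, serious, at least 10% incidence) excluding the PEx term and component-sign events linked to a PEx. Keep PEx incidence as its own safety evaluation.

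**Data already entered.** Link an event to a PEx only if it is one of the 12 listed signs, falls within the episode and is judged not drug-related. Episode dates alone would also remove drug-caused events that began during an episode.

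**Cost.** An e-CRF completion note, a short linking rule, and one extra run of existing tables. No information is lost, because the all-TEAE tables remain.
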